1. BACKGROUND

Organized ventricular arrhythmias (ventricular tachycardia (VT), torsades de pointes (TdP) and ventricular fibrillation (VF)) represent a major event in the clinical history of a patient and they can lead to hemodynamic instability and sudden cardiac death (SCD).

Organized ventricular arrhythmias may be associated with structural heart disease (either with ischemic or non-ischemic etiology), genetic arrhythmic syndromes (Brugada syndrome, familial long QT syndrome, right ventricular arrhythmogenic cardiomyopathy) or metabolic disorders. Nonetheless, the etiology of ventricular arrhythmias may remain unknown even after extensive diagnostic workup.

In patients at high risk for ventricular arrhythmias, the guidelines of European Society of Cardiology¹ suggest the implant of an internal defibrillator (ICD), a subcutaneous device that can quickly recognize and treat arrhythmias using fast ventricular pacing (ATP) or internal shock.

Patients that have already had an organized ventricular arrhythmia with hemodynamic instability are considered at high risk for SCD and ICD implant is therefore suggested (secondary prevention). Patients with structural heart disease and severe impairment of contractile function are considered as well at high risk for SCD and an ICD implant is suggested (primary prevention).

Recurrences of ventricular arrhythmias and electrical instability have exponentially increased in the last decades and a new clinical entity called “electrical storm” (ES) has emerged as major morbidity and mortality factor. The ES is defined as a cluster of 3 or more sustained ventricular arrhythmias within 24 hours, or a sustained ventricular tachycardia lasting 12 hours or more and that does not respond to treatments².

Most of the patients presenting ES are already implanted with an ICD. This is due to 3 factors: first, patients with ICD implant are at higher risk to develop ventricular arrhythmias for the cardiac disease that led to the ICD implant. Second, the device records and treats also asymptomatic or poor symptomatic arrhythmic episodes that otherwise would not be detected. Third, and more important, the device gives the possibility to survive to an arrhythmic episode, making it possible for the patient to experience an ES.

The incidence of ES is debated in different studies and ranges from 10 to 60% in patients with ICD for secondary prevention and from 4 to 7% in patients with ICD for primary prevention³.

2. AIM OF THE STUDY

The aim of the ELECTRA registry is twofold:

- a) To create an international registry on clinical features, optimal therapy, ablation strategy, prognosis and the effect of ICD programming on patients with ES.
- b) To use the data derived from the registry for a prospective, observational study on mortality and rehospitalization rate in patients with ES.

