4.2 SECONDARY ENDPOINT

- Hospitalization for all causes 3 years after the ES

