4.3 ANALYSIS OF RELAPSES AND MORTALITY

Each center will be asked to report every new hospital admission of patients enrolled in the study and the cause of hospitalization. Moreover, data about subjects' vital status will be asked to be updated every 6 months.

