4.4 STATISTICAL ANALYSIS

The primary endpoint will be estimated annually and it will be expressed as absolute and relative numbers. Survival curves free from study endpoint, eventually divided into subgroups according to variables of interest such as gender, age, underlying heart disease, comorbidity and programming mode, will be drawn with Kaplan-Meier method and compared by Log-rank test. Basal and follow-up parameters (clinical, electrocardiographic and echocardiographic) will be compared by χ^2 test or by Fisher test if they are discrete; by T-student test or signed rank test if they are continuous. Every test will be two-tailed and a value of $p>0.05$ will be considered significant.

According to the number of centers involved we expect to recruit at least 500 patients. Considering an annual incidence of the primary endpoint (death from all causes) of 11% according to our experience (Guerra et al. Europace 2015), we expect about 55 events at the first statistical analysis after one year from the start and we expect about 165 events at the end of the follow-up of three years. The statistical analysis will be conducted using the SPSS 21.0 for Windows software (SPSS Inc. Chicago, IL, USA).

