
4.0 - Follow Up
 
Last follow-up date  - Vital status at last follow-up  - Number of total ES recurrences  - First ES recurrence date  Number of total VT/VF recurrences  - First VT/VF recurrence date  - Number of total HF rehospitalizations  - First HF rehospitalization date 

 

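### The aim names a rehospitalization rate and every admission is to be reported, but no stated analysis uses repeat admissions or gives admissions per patient-year

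*Combined protocol and SAP*

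**What the plan says.** All references are to the combined protocol and SAP.

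- **Section 2, aim (b):** a "prospective, observational study on mortality and rehospitalization rate in patients with ES". *Rate* is not defined.
- **Section 4.2:** the secondary endpoint is "Hospitalization for all causes 3 years after the ES". It does not say whether this means the first admission, any admission (yes or no) or the number of admissions.
- **Section 4.3:** "Each center will be asked to report every new hospital admission of patients enrolled in the study and the cause of hospitalization". The section title promises an analysis of relapses, but the text covers reporting only.
- **Section 4.4:** "The primary endpoint will be estimated annually and it will be expressed as absolute and relative numbers". No matching sentence covers the secondary endpoint. The event-time analysis is "Survival curves free from study endpoint, eventually divided into subgroups according to variables of interest" (gender, age, heart disease, comorbidity, programming mode); these curves "will be drawn with Kaplan-Meier method and compared by Log-rank test".
- **Attachment #3, follow-up block:** the only hospitalization items are "Number of total HF rehospitalizations" and the date of the first heart-failure rehospitalization. Attachment #4 likewise lists heart failure only.

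**The concern.** The hospitalization outcome changes its unit from section to section: a rate in the aim, an endpoint at 3 years in 4.2, every admission in 4.3 and an event-free curve in 4.4. In an event-free curve a patient leaves the risk set at the first event, so one admission and six admissions count the same.

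Two things are at stake. First, if *rate* means admissions per unit of time, the plan does not produce the quantity named in its aim. Second, section 3 argues that the sample is large enough for subgroup analyses and 4.4 names the subgroups. A comparison limited to first admissions can have clearly less power than one using all the admissions that centers are asked to report.

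**Working it through.** **1. Does any stated analysis use a repeat admission?**

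- Annual absolute and relative numbers (4.4): primary endpoint only, which is death.
- Kaplan-Meier with log-rank (4.4): first event per patient, if hospitalization is covered at all. The term study endpoint is singular and follows a sentence on the primary endpoint.
- χ², Fisher, t and signed rank tests (4.4): for baseline and follow-up clinical, ECG and echo parameters. Hospitalization is not named.
- Yearly descriptive report (3.3): risk factors, management, laboratory and imaging values, and storm variables. Hospitalization is not listed.

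None uses second or later admissions, and none yields admissions per patient-year.

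**2. The plan's own figures.** 500 × 0.11 = 55 deaths at one year and 500 × 0.11 × 3 = 165 at three years; both match 4.4. With the risk set shrinking, the 3-year figure would be 500 × (1 − 0.89³) = 147.5. These figures concern deaths and do not test the present point. No figure is stated for hospitalization.

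**3. Share of admissions that are not a patient's first.**

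From the documents: 500 patients, 3 years, 11% annual mortality, so death hazard μ = −ln(0.89) = 0.1165 per year. Assumed: admission rate λ per patient-year, gamma frailty with variance θ, and admissions independent of death.

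- Time alive per patient = (1 − 0.89³)/0.1165 = 0.2950/0.1165 = 2.532 years. For 500 patients this is about 1,266 patient-years.
- All admissions = 1,266 × λ.
- First admissions = 500 × ∫₀³ λ(1 + θλt)^(−1/θ − 1) e^(−μt) dt. For θ = 0 this is 500 × λ/(λ + μ) × (1 − e^(−3(λ + μ))).

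Example, λ = 0.1 and θ = 0: 500 × (0.1/0.2165) × (1 − e^(−0.6496)) = 110 first admissions among 127, so 13% are not first.

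| λ | All admissions | Not first, θ = 0 | θ = 1 | θ = 2 |
|---|---|---|---|---|
| 0.1 | 127 | 13% | 22% | 29% |
| 0.3 | 380 | 32% | 45% | 53% |
| 0.5 | 633 | 46% | 58% | 65% |
| 1.0 | 1,266 | 66% | 73% | 78% |
| 1.2 | 1,519 | 71% | 76% | 80% |

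The share passes 50% only above about 0.57 (θ = 0), 0.36 (θ = 1) or 0.26 (θ = 2) admissions per patient-year.

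**4. Power for a subgroup comparison (simulation).** Two groups of 250, an assumed rate ratio of 1.3, two-sided 5% tests, same mortality and follow-up. The rate is that of the reference group; the other group has 1.3 times it, so totals here are 1.15 times those in the table.

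- Reference rate 0.3 to 1.2, θ = 0.5 to 2: about 22% to 48% for log-rank on first admission, against 38% to 88% for a rate comparison on all admissions with robust variance. Repeat runs move these ends by a point or two.
- Reference rate 0.5, θ = 1: about 31% to 37% across runs, against 59% to 60%.
- Reference rate 0.1: the gap is small, for example 20% against 28% at θ = 1.
- With no true difference, both methods rejected in 4% to 8% of runs (500 simulations per scenario).

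**The case against.** The strongest reply is that *rate* may mean the proportion of patients rehospitalized by 3 years. That would parallel mortality, which 4.4 gives as absolute and relative numbers, and it fits the wording of 4.2. One minus the Kaplan-Meier curve would then address the aim, apart from the treatment of death: censoring deaths overstates the proportion. This stands. A reader might infer that the rate in aim (b) is never estimated, but the documents support that only for admissions per patient-year.

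A reader might also infer that the plan throws away most of the admissions it collects. The documents give no admission rate, and under the assumptions above the share falls on either side of one half.

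Nor do the documents show that the sponsor chose a first-admission endpoint. Section 4.2 does not say so; it follows only from the Kaplan-Meier method, and only if the curves cover hospitalization. If they do not, the gap is wider, because the secondary endpoint then has no stated analysis.

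Finally, the registry is described as exploratory, without a statistical sample size calculation, and no subgroup effect on hospitalization is hypothesised. The rate ratio of 1.3 is therefore an illustration. Time to first admission is an accepted estimand, so replacing it with a count would be a trade-off and not a correction. This stands, and it argues for adding an analysis beside the curve.

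**Conclusion.** The point holds in limited form. Under every reading of 4.2 and 4.4, no stated analysis uses repeat admissions or gives admissions per patient-year, although 4.3 requests every admission and the aim speaks of a rate that is left undefined. This needs no assumption.

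The size does. Over 0.1 to 1.2 admissions per patient-year and frailty variance 0 to 2, between 13% and 80% of admissions are not a patient's first. The gain in power is material from about 0.3 per patient-year upward and small at 0.1. These figures also assume that admissions are independent of death, which may not hold in this population.

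For a secondary endpoint in an observational registry, this should be put right, but it does not threaten the primary analysis of mortality.

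**What to change.** - **Section 4.2:** state that all-cause hospitalization within 3 years of the storm is assessed both as first admission and as all admissions. Say which of these the word *rate* in aim (b) refers to.
- **Section 4.4:** keep time to first admission. Add the all-cause admission rate per 100 patient-years alive and under observation with a 95% CI, and the mean cumulative number of admissions with death as a terminal event.
- **Subgroups:** compare all admissions by a negative binomial model with log follow-up time as offset, or by a recurrent-event rate model with robust variance. Report the results beside mortality, because death shortens the time at risk.
- **Forms:** add dated all-cause admission entries to the follow-up block of Attachment #3 and to Attachment #4. Both now hold heart-failure rehospitalizations only, so they do not carry what 4.3 requests.

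**Cost:** a few sentences in the plan, new form fields and some added analysis, with no new patients or procedures. Section 3.2 allows retrospective inclusion, so admissions of those patients between the storm and consent must come from existing records and may be incomplete. The rate must be read together with mortality.

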3. REGISTRY DESIGN

The creation of the present registry is aimed at gathering information on a wide cohort of patients affected by ES. All patients will be enrolled for a minimum of three years from the protocol approval. There is no pre-specified date for the end of enrollment, which will be decided by the study responsible according to the enrollment rate.

A minimum of 500 patients will be included in the present registry. The exploratory nature intrinsic to the registry characteristics does not allow a sample size calculation by statistical means. However, the sample presented is based on the estimated enrolment rates of the participating centers during a 3-year enrolment period. Moreover, the sample size is large enough to postulate specific subgroup analyses.

REGISTRY INCLUSION CRITERIA:

- Diagnosis of ES (documentation of 3 or more episodes of sustained ventricular arrhythmia within 24h or documentation of sustained ventricular tachycardia lasted at least 12h). In order to fulfill this criterion, a patient with a previous episode of ES could also be enrolled during routine screening.
- Age ≥ 18
- Written informed consent

REGISTRY EXCLUSION CRITERIA:

- patient without ICD
- Confirmed or suspected use of drugs or narcotics with known direct pro-arrhythmic effect
- Inability to express an informed consent for the study

At enrollment, each patient will be informed on the aim and the design of the study, and the investigations needed. All patients that meet the inclusion criteria will be included in the study (attachment #1). All recruited patients will receive the informative form (attachment #1) and the informative letter to their general practitioner (attachment #2).

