3.1 EVALUATION OF ELIGIBILITY

All patients admitted to the participating centers will be evaluated consecutively by the referent investigators. All patients that meet the above-described criteria will be included in the registry.

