3.2 DATA COLLECTION

No additional procedures are required to the participating centers. Data usually collected in the center and necessary for the analysis will be collected by the referent investigator. Considering that ICDs record the principal events of the whole life of the device, patients with an ES previous to the creation of this registry will be included retrospectively providing that:

- 1) clinical data from the participating center are complete and accurate and allow to check inclusion and exclusion criteria
- 2) follow-up is available
- 3) ICD has not been replaced, leading to the loss of original data
- 4) ECG and echocardiography done in routine practice are available in case of necessity
- 5) subject agrees to subscribe the informed consent during the next routine visit in the recruiting center

All data will be used with scientific research purposes only. Data will be saved on a dedicated website⁷ in agreement with current regulations on the treatment of personal data. Electronic cards of data collection transmitted to the study responsible will be identified by an alphanumeric code. The list of matches between subjects' data and these codes will be created and kept by local investigators or delegates. The data manager is the study responsible.

For the type of data requested, see Case Report Form (attachment #3)

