4. OBSERVATIONAL STUDY DESIGN

Multicenter, observational, prospective clinical study. Data from the first 500 patients enrolled in the registry will be used for the present analysis. Please see point #3 of the present protocol for information regarding registry enrollment criteria and data collection.

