4.1 PRIMARY ENDPOINT

- All-cause mortality 3 years after the ES

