5. INDICATIONS OF EXPECTED RISKS AND BENEFITS FOR SUBJECTS IN THE STUDY

As no procedures or therapies are required there are no expected risks for patients participating to the registry. Despite no short-term benefits will be granted to any of participating patients, increasing knowledge of ES will bring to future benefits to the community, especially concerning the capacity to prevent recurrent shocks in ICD bearers.

Each subject will be informed both orally and by an appropriate document concerning procedures and purposes of the study. It will be clearly explained that participating (or not

participating) to the study will not change the frequency and type of clinical evaluations expected for the subject's disease. Patients can consult people they trust and they will have enough time to identify and ask any criticism and to gather further information; finally, patients will be asked to sign the informed consent if they agree to participate to the present registry. It will be stated that patient's participation to the registry is voluntary, free and that the consent can be withdrawn at any time and for any reason.

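### Admitted ES patients who die before consent, or never regain capacity, cannot be enrolled and are not counted, so 3-year mortality timed from the ES describes only those who survived to consent

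*Combined protocol and SAP*

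**What the plan says.** All references are to the combined protocol and SAP.

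- **Entry.** Section 3 lists "Written informed consent" among the inclusion criteria and "Inability to express an informed consent for the study" among the exclusions. Section 5 describes consent by the patient: "patients will be asked to sign the informed consent if they agree to participate to the present registry".
- **Screening.** Section 3.1 states that "All patients admitted to the participating centers will be evaluated consecutively by the referent investigators", and that those who meet the criteria are included.
- **Later entry.** Section 3 adds that "a patient with a previous episode of ES could also be enrolled during routine screening". Section 3.2 allows retrospective inclusion provided that the "subject agrees to subscribe the informed consent during the next routine visit in the recruiting center".
- **Endpoint and analysis set.** The primary endpoint in section 4.1 is "All-cause mortality 3 years after the ES". Section 4 says "Data from the first 500 patients enrolled in the registry will be used for the present analysis".
- **Silent points.** No section gives a time at which capacity to consent is judged. No log of eligible patients left out is described, and section 4.3 asks for follow-up of enrolled patients only. The case report form (Attachment #3) records ES start and end dates but no consent or enrolment date. Section 4.4 plans no sensitivity analysis for deaths before consent.

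**The concern.** The clock for the primary endpoint starts at the storm, but a patient can be counted only after giving consent. Deaths between those two moments are the earliest deaths, and entry by personal consent removes them from the analysis set. The loss falls on patients who die before they can be asked and on those who stay incapacitated.

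This is foreseeable. Section 1 describes haemodynamic instability and sudden death as consequences of these arrhythmias, and Attachment #3 (item 2.3) lists sedation among the acute treatments.

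At stake is the meaning of the main result. Aim (b) in section 2 concerns mortality in patients with ES. What the plan would deliver is mortality among those who lived long enough, and recovered enough, to sign. The two differ in a known direction by an unknown amount, and as written the registry would hold no data from which to judge that amount. Enrolling more patients would not reduce the gap.

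**Working it through.** **1. The plan's own figures (section 4.4).** Inputs: N = 500 and 11% mortality a year.

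- One year: 500 × 0.11 = 55, as stated.
- Three years: 500 × 0.11 × 3 = 165, as stated. That is 165/500 = 33.0%.
- The 165 is a linear product. Compounding gives 1 − 0.89³ = 0.295, or 147.5 deaths in 500. Both 33.0% and 29.5% are carried forward as values of m.

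This point does not show any stated figure to be wrong.

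**2. Formula.** Let f be the share of otherwise eligible prospective admissions who die before consent, and m the 3-year mortality in enrolled patients. If the remaining patients have mortality m, then

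- mortality after the ES = f + (1 − f) × m
- shortfall in the reported figure = f × (1 − m)
- uncounted early deaths per 500 enrolled = 500 × f / (1 − f)

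**3. Results.** The documents do not give f. The values below are assumptions.

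| Assumed f | After the ES, m = 29.5% | Shortfall (points) | After the ES, m = 33.0% | Shortfall (points) | Uncounted deaths per 500 enrolled |
|---|---|---|---|---|---|
| 2% | 30.9% | 1.4 | 34.3% | 1.34 | 10.2 |
| 5% | 33.0% | 3.5 | 36.4% | 3.35 | 26.3 |
| 10% | 36.6% | 7.0 | 39.7% | 6.70 | 55.6 |

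Example: f = 5% and m = 29.5% gives 0.05 + 0.95 × 0.295 = 0.330, and 0.05 × 0.705 = 0.035.

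**4. Comparison with sampling error.** With m = 33%, the 95% half-width is 1.96 × √(0.33 × 0.67 / 500) = 4.1 points. The shortfall equals it at f = 4.12/67 = 6.2%. With m = 29.5%, the half-width is 4.0 points and the threshold is f = 5.7%.

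**5. What the formula leaves out.** It covers deaths before consent only. Patients who survive but never regain capacity, and patients who refuse, are also missing from the 500. Their mortality is unknown and is not modelled here. The table also treats all 500 as prospective admissions, whereas sections 3 and 3.2 let patients with a past ES in as well.

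**The case against.** **Sedated patients.** A reader might infer that sedated patients are lost as a group. The documents do not support that. The exclusion sets no time for judging capacity, and section 3 lets a patient with a previous ES enrol later. A sedated patient who recovers stays enrollable. The sedation field in Attachment #3 is completed for enrolled patients, which suggests that sedation was not meant to bar entry. This part of the objection stands in full.

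**A sedation subgroup.** A reader might also infer that a planned comparison by sedation is stripped of its worst cases. Section 4.4 does not name sedation among its example subgroups, and section 3.3 treats acute management descriptively.

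**Size.** The values of f are assumed. Section 4.4 attributes the 11% to the group's experience, and the documents do not show whether that cohort already counted early deaths, so using it for consented patients is itself an assumption. Shortfalls at f = 2% and 5% lie within sampling error. The population is restricted to ICD carriers, and section 1 says the device treats episodes with few or no symptoms and helps patients survive, which is a reason to doubt the largest value. All this stands, and it limits the size rather than the mechanism.

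**Ordinary practice.** Requiring personal consent is a normal ethical choice for an unfunded registry that adds no procedures, and section 4 openly limits the analysis to enrolled patients. That is fair, but the endpoint is still worded as mortality after the ES. The STROBE commitment in section 3.3 does not itself set up a record of those left out.

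**Repair by analysis alone.** Delayed entry at consent would deal with the survivor time of late consenters, although the form has no consent date to support it. It would not recover the missing patients, because late or absent consent reflects severity as well as time.

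**Consent form.** Attachment #1 is not in the reviewed text, so it cannot be said that no proxy or deferred consent exists anywhere. The section 3 exclusion stands as written.

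**Conclusion.** The point holds for prospectively admitted patients. Following the plan as written, deaths before consent cannot enter the primary estimate, so it understates 3-year mortality after the ES by f × (1 − m). For assumed f of 2% to 10%, that is about 1.3 to 7.0 percentage points across the two values of m. It exceeds the 95% half-width only once f passes roughly 6%. The direction follows from sections 3, 4 and 4.1. The size rests on assumed f, on taking 29.5% or 33% as mortality in enrolled patients, and on ignoring refusals and persistent incapacity among survivors.

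A reader might go further and infer that centers will apply the exclusion differently, some on the first day and some only after recovery. The text leaves room for this because no timing is set, but nothing in it shows that it will happen. Nor is it established that the true shortfall is large. That no count is described is the reason to start one.

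**What to change.** 1. **Section 3.** State that inability to consent is judged up to discharge, so that temporary incapacity alone does not exclude. Leave the consent route to the ethics committee.
2. **Section 3.1 and Attachment #3.** Within the consecutive evaluation already required, have each center keep an anonymous count of all otherwise eligible ES admissions not enrolled, by reason: death before consent, persistent incapacity, or refusal. Record vital status at discharge where the ethics committee allows it. Add the consent date to the case report form.
3. **Sections 4.1 and 4.4.** Label the primary estimate as mortality among patients who survived to consent. Add a sensitivity analysis restricted to prospective admissions, with every logged non-enrolled eligible patient in the denominator, both deaths and those discharged alive. Give bounds for the unknown later outcomes of those discharged alive, from all surviving to 3 years to all dying. Adding only the pre-consent deaths would push the figure upward, because the matching non-enrolled survivors would be left out.

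Cost: a wording amendment, ethics approval for the log (it concerns people who have not consented), one extra form field and a small amount of center work. The headline mortality would probably look less favourable. The log should start early, since uncounted deaths are hard to recover afterwards.
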